2.2. Study Outcomes

2.2.1. Primary Outcomes

- The utility-weighted modified Rankin Scale (mRS) at 90 days, comparing patients found eligible for tPA (based on a blinded review of the patient's chart, regardless of whether they were treated or not) on MSU weeks compared to patients on SM weeks.

2.2.2. Secondary Outcomes

- Comparing patients found eligible for tPA (based on a blinded review of the patient's chart, regardless of whether they were treated or not) on MSU weeks compared to patients on SM weeks.
 - ordinal (shift) analysis of mRS at 90 days, and
 - proportion of patients achieving 90-day mRS 0,1 vs 2-6
 - 30% improvement from baseline to 24hr NIHSS
- The agreement between the VN on board the MSU with a VN remotely assessing a suspected stroke patient for treatment with tPA via TM in the MSU, and the rate of technical failures in conducting the TM consultation. N.B. Patients will include all enrolled patients on MSU weeks considered for tPA treatment.
- An exploratory cost-effectiveness analysis (CEA) of MSU versus SM using the Incremental Cost Effectiveness Ratio and Incremental Net Benefit estimate will be performed. N.B. The exploratory CEA will include all enrolled patients on MSU and SM weeks found eligible for tPA (based on a blinded review of the patient's chart, regardless of whether they were treated or not)

- Comparing all patients treated with tPA (whether or not adjudicated as tPA eligible) on MSU weeks compared to patients on SM weeks.
 - Utility-weighted modified Rankin Scale (mRS) at 90 days
 - ordinal (shift) analysis of mRS at 90 days, and
 - proportion of patients achieving 90-day mRS 0,1 vs 2-6
 - 30% improvement from baseline to 24hr NIHSS
- Comparing enrolled patients treated with tPA within 60 minutes of LSN onset according to published guidelines on either MSU or SM weeks, compared to similar patients treated 61-270 minutes after onset, adjusting for any imbalances in stroke severity (baseline NIHSS) between the groups at the time of treatment. N.B. Patients will include only those patients actually treated with tPA based on the final determination of the time LSN, and will include only patients meeting all inclusion and exclusion criteria.
 - utility-weighted mRS at 90 days,
 - ordinal (shift) analysis of mRS at 90 days
 - proportion of patients achieving 90-day mRS 0,1 vs 2-6
 - 30% improvement from baseline to 24hr NIHSS
 - Instead of dichotomizing into two groups based on time from LSN to tPA, logistic regression of 90-day mRS 0,1 vs 2-6, using a restricted cubic spline for time from onset to treatment, with visualization of spline term compared with the odds ratio
- Comparing all patients treated with IAT (separate analyses for those adjudicated as tPA eligible, all tPA treated, or all IAT with or without tPA) on MSU weeks compared to patients on SM weeks.
 - utility-weighted mRS at 90 days
 - ordinal (shift) analysis of mRS at 90 days
 - proportion of patients achieving 90-day mRS 0,1 vs 2-6
 - 30% improvement from baseline to 24hr NIHSS
- The time from LSN to tPA treatment on all patients treated within 4.5 hours of LSN on MSU weeks compared to similarly eligible patients on SM weeks. N.B. Patients will include all enrolled patients actually treated with tPA (or on SM weeks, eligible for tPA treatment) meeting all inclusion and exclusion criteria, and based on the final determination of time of LSN. One analysis will compare the median times. A second analysis will also capture the patients who were eligible but did not receive tPA because it was too late, categorizing time into the following groups (e.g., 0-60min, 61-90min, 91min-180min, 181-270min, eligible but no tmt because>270).
 - Of the enrolled patients that were eligible for treatment with tPA (according to

published guidelines) on MSU weeks compared to SM weeks, the percent that were treated within 4.5 hours and within 60 minutes of LSN.

- The time from LSN, from alarm time, and from ED arrival to start of endovascular procedure (intra-arterial thrombectomy-IAT) in patients who meet pre-specified criteria for IAT on MSU weeks compared to SM weeks. N.B. All patients receiving IAT will be included in this outcome.
- The proportion of all tPA-eligible patient having IAT on MSU weeks compared to SM weeks
- The median/mean time from LSN to tPA therapy decision on all patients considered for treatment within 4.5 hours of LSN on MSU weeks compared to SM weeks. N.B. Patients will include all enrolled patients meeting inclusion criteria whether or not treated with tPA.
- Time between 911 call and onset of etiology-specific BP management on MSU weeks compared to SM weeks. N.B. Patients will include all enrolled patients.

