b. proportion of patients achieving 90 day mRS 0.1 vs 2-6

- 6. comparing patients found eligible for tPA (based on a blinded review of the patient's chart, regardless of whether they were treated or not) onMSU compared to SM weeksThe time from LSN to tPA treatment on all patients treated within 4.5 hours of LSN onMSU weeks compared to similarly eligible patients on SM weeks. N.B. Patients will include all enrolled patients actually treated with tPA (or on SM weeks eligible for tPA treatment) meeting all inclusion and exclusion criteria, and based on the final determination of time of LSN. One analysis will compare the median times. A second analysis will also capture the patients who were eligible but did not receive tPA because it was too late, categorizing time into the following groups (e.g., 0-60min, 61-90min, 91min-180min, 181-270min, eligible but no tmt because>270).
- Of the enrolled patients that were eligible for treatment with tPA (according to published guidelines) on MSU weeks compared to SM weeks, the percent that were treated within 4.5 hours and within 60 minutes of LSN.
- 8. The time from LSN and from ED arrival to start of endovascular procedure (intra-arterial thrombectomy-IAT) in patients who meet pre-specified criteria for IAT onMSU weekscompared to SM weeks.

 N.B. All patients receiving IAT will be included in this outcome.
- The median/mean time from LSN to tPA therapy decision on all patients considered for treatment within 4.5 hours of LSN on MSU weeks compared to SM weeks. N.B. Patients will include all enrolled patients meeting inclusion criteria whether or not treated with tPA.
- Time between 911 call and onset of etiology-specific BP management on MSU weekscompared to SM weeks. N.B. Patients will include all enrolled patients.

Safety endpoints

1. The incidence of symptomatic intracranial hemorrhage (sICH) in enrolled tPA treated ptients on MSU weeks compared to SM weeks (Symptomatic intracranial hemorrhage defined as any intracranial blood accumulation associated with a clinical deterioration of \geq 4 points of the NIHSS for which the hemorrhage

- has been identified as the dominating cause of the neurologic deterioration) **N.B.** Patients will include all patients treated with tPA, whether or not they meet all inclusion and exclusion criteria.
- **2.** Mortality. **N.B.** All enrolled patients signing informed consent will be included in this endpoint and followed until 1 year.

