5.D. Blinded adjudication: All enrolled patients are reviewed by a VN blinded to assignment of MSU vs SM management and not involved with either MSU or remote TM patient management. The blinded VN determines from a dedicated "adjudication form" that is missing any time data or other information that would produce unblinding, if the patient meets criteria for study enrollment and for tPA treatment. If the patient is enrolled or considered to be a "tPA-eligible patient" by either the MSU or SM

enrolling team, but do not meet criteria after adjudication, they will not be included in data analysis of the primary outcome. If an enrolled patient meets criteria for tPA but is not treated, that fact will be noted, the patient considered a "miss", and the patient will still be followed and outcomes measured. For comparing the primary outcomes between MSU and SM, we will only include tPA-eligible patients in both the MSU and SM groups, whether or not actually treated, based on this blinded review.

- **5.E. BP**: On both MSU and SM weeks, blood pressure is measured at baseline and thereafter according to EMS routine, and treated to target levels, according to published guidelines for ischemic stroke, pre and post-tPA treatment, and for intracerebral hemorrhage. The time of first BP treatment is recorded.
- **5.F. CT:** A cerebral CT scan must be performed on all patients meeting Inclusion Criteria for IV tPA, and the CT scan must be read by the MSU VN prior to the initiation of tPA treatment. Follow up CT or MRI imaging is optional as is the timing. It is carried out as per routine care and results recorded if done. CT or MRI are immediately performed in the case of neurological deterioration.
- **5.G. TM:** The TM connection is Health Insurance Portability and Accountability Act (HIPAA) compliant and encrypted. VNs connect to the device from a desktop computer. Connections are encrypted using a combination of RSA public/private key and 256-bit advanced encryption standard symmetrical encryption to ensure confidentiality of patient information transmitted.

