of enrolled patients treated with tPA within 60 minutes of LSN onset according to published guidelines on either MSU or SM weeks, compared to similar patients treated 61-270 minutes after onset, adjusting for any imbalances in stroke severity (baseline NIHSS) between the groups at the time of treatment. **N.B.** Patients will include only those patients actually treated with tPA based on the final determination of the time LSN, and will include only patients meeting all inclusion and exclusion criteria.

- 6.A.3. a. ordinal (shift) analysis of mRS at 90 days, and
 - b. proportion of patients achieving 90 day mRS 0,1 vs 2-6

comparing patients found eligible for tPA (based on a blinded review of the patient's chart, regardless of whether they were treated or not) on MSU weeks compared to SM weeks.

- **6.A.4.** The time from LSN to tPA treatment on all patients treated within 4.5 hours of LSN on MSU weeks compared to similarly eligible patients on SM weeks. **N.B.** Patients will include all enrolled patients actually treated with tPA (or on SM weeks, eligible for tPA treatment) meeting all inclusion and exclusion criteria, and based on the final determination of time of LSN. One analysis will compare the median times. A second analysis will also capture the patients who were eligible but did not receive tPA because it was too late, categorizing time into the following groups (e.g., 0-60min, 61-90min, 91min-180min, 181-270min, eligible but no tmt because>270).
- **6.A.5.** Of the enrolled patients that were eligible for treatment with tPA (according to published guidelines) on MSU compared to SM weeks, the percent that were treated within 4.5 hours and within 60 minutes of LSN.
- **6.A.6.** The time from LSN and from ED arrival to start of endovascular procedure (intra-arterial thrombectomy-IAT) in patients who meet pre-specified criteria for IAT on MSU weeks compared to SM weeks. **N.B.** All patients receiving IAT will be included in this outcome.
- **6.A.7.** The median/mean time from LSN to tPA therapy decision on all patients considered for treatment within 4.5 hours of LSN on MSU weeks compared to SM weeks. **N.B.** Patients will include all enrolled patients meeting inclusion criteria whether or not treated with tPA.
- **6.A.8.** Time between 911 call and onset of etiology-specific BP management on MSU weeks compared to SM weeks. **N.B.** Patients will include all enrolled patients.
 - 6.B. Safety Outcomes for S.A. 1

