6.5. Process Analysis

Time from alarm to treatment decision will be compared using a one-sided Wilcoxon rank sum test ($\alpha=0.05$) to test if the time is longer for the MSU arm. This will be conducted on the subset that are tPA-eligible based on the blinded adjudication. MSU-by-site interaction terms will be included in a regression model to test if these differ by site and if the interactions are

significant then within-site tests will be conducted.

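### Time from last seen normal to tPA: the stated population is treated patients on MSU weeks but eligible patients on SM weeks, and no rule covers eligible patients who are never treated

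*SAP*

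**What the plan says.** SAP 2.2.2 introduces the outcome as the time to tPA in "all patients treated within 4.5 hours of LSN on MSU weeks compared to similarly eligible patients on SM weeks". Its note repeats the split: "Patients will include all enrolled patients actually treated with tPA (or on SM weeks, eligible for tPA treatment) meeting all inclusion and exclusion criteria". The Protocol synopsis (secondary endpoint 6) has the same wording, "actually treated with tPA (or on SM weeks eligible for tPA treatment) meeting all inclusion and exclusion criteria", and so does Protocol 6.A.4, with the parenthesis "or on SM weeks, eligible for tPA treatment".

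Three analyses are planned:

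- **Medians.** The two arms' median times are compared.
- **Time categories.** "A second analysis will also capture the patients who were eligible but did not receive tPA because it was too late"; these patients get a row for more than 270 minutes. The sentence names no arm.
- **Cox model.** Protocol 7.C and SAP 5.1.4 plan a Cox model for time to treatment, handled like survival. Neither gives a censoring time or says how a patient who never receives tPA enters the model.

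Both arms can contain such patients. Protocol 5.C.3 keeps an MSU patient eligible if IV access or another technical step fails on board. Protocol 5.C.4 keeps an SM patient eligible if the window has passed or the deficit has resolved by the time of full ED evaluation. Protocol 5.D names no arm: "If an enrolled patient meets criteria for tPA but is not treated, that fact will be noted".

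Neighbouring outcomes use one rule for both arms. For time to therapy decision, SAP 2.2.2 says "Patients will include all enrolled patients meeting inclusion criteria whether or not treated with tPA". For alarm-to-decision time, SAP 6.5 says "This will be conducted on the subset that are tPA-eligible based on the blinded adjudication". Percent treated uses all eligible patients in both arms.

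**The concern.** Read literally, an eligible MSU patient who gets no tPA leaves the analysis, while an eligible SM patient who gets no tPA stays in it. In a Cox model the retained SM patients lengthen the SM risk sets without adding events, so SM looks slower even if care is identical. Ranking them last in a median, or putting them in the row above 270 minutes, works in the same direction.

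Earlier treatment is the mechanism through which the trial expects benefit, so this estimate will be read closely. SAP 5.1.4 generally prefers confidence limits to tests for ancillary outcomes. That does not protect against the problem, because the interval itself shifts.

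**Working it through.** The documents give no effect size or power for this outcome, so there is no planned figure to reproduce. The check asks how far the stated rule can move the HR.

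**Inputs from the documents.** SAP 2.1 and 4.1 give 1038 eligible patients at 1.5:1, that is 1038 × 0.6 ≈ 623 MSU and 1038 × 0.4 ≈ 415 SM. The treatment window is 270 minutes. In the run-in (Protocol 4.C), 13 MSU patients were treated and the 12 untreated patients had listed reasons that show no evident eligible miss. Protocol 1.A cites a 25-minute gain from a German MSU.

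**Assumptions.** The untreated shares u_M (MSU) and u_S (SM) are not given and are varied. LSN-to-tPA times are lognormal, truncated at 270 minutes, with median/log-SD of 100/0.4, 80/0.5 and 120/0.35. Untreated status is random. Untreated patients are censored either at 270 minutes or at an ED decision time drawn from the same distribution as the treatment times.

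**Formula.** Let f and S be the density and the share still waiting among MSU patients who are treated.

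- MSU hazard as written (untreated dropped): f/S.
- MSU hazard in a common eligible set, censored at 270: (1−u_M)f / [(1−u_M)S + u_M].
- As-written HR divided by common-set HR at a given time: 1 + u_M / [(1−u_M)S].
- With ED-time censoring the same ratio is 1/(1−u_M).

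The SM hazard cancels, so the distortion depends on the MSU untreated share. At u_M = 1%, 0.01/0.99 = 0.0101, and the 270-minute ratio is 1.010 at S = 1, 1.020 at S = 0.5 and 1.101 at S = 0.1. With ED-time censoring it is 1/0.99 = 1.010.

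**Simulated Cox results, 623 against 415, identical treatment times.** Distortion is as-written HR divided by common-set HR.

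| MSU / SM untreated | Distortion, 270 min | Distortion, ED time |
|---|---|---|
| 0% / 5% | 1.00 | 1.00 |
| 1% / 5 to 10% | 1.05 | 1.01 |
| 5% / 5% | 1.22–1.23 | 1.05 |
| 10% / 10% | 1.42–1.43 | 1.11 |

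In the last two rows care is identical and the common-set HR is 1.00, so the distortion is the whole apparent effect. In the first row the SM shortfall is a real difference between arms, not an artefact. A separate simulation used the run-in time categories and censoring at 270. It gave HR 1.22 at 5% and 1.43 at 10%, with the 95% interval excluding 1 in 87% and 100% of trials. With one common set the HR was 1.00 and the interval excluded 1 in 4 to 5%.

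**Median.** Over observed times in both arms there is no shift. If SM untreated patients are ranked last, the SM median moves to the 0.5/(1−u_S) quantile. At 5% that is 0.5/0.95 = 0.526. On the run-in distribution the median is then 77.1 minutes against 75.0.

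**How large could u_M be?** Zero of 13 has an exact 95% upper limit of 1 − 0.025^(1/13) = 24.7%. The run-in suggests a low share but does not establish it.

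**With a true 25-minute gain, censoring at 270:**

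| MSU / SM untreated | As written | Common set | Treated-only, both arms |
|---|---|---|---|
| 1% / 5% | 2.06–2.21 | 1.89–2.02 | 1.79–1.94 |
| 10% / 10% | 2.32–2.47 | 1.43–1.49 | 1.80–1.94 |

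The direction does not change. At 10%, part of the gap between as-written and common-set comes from censoring at 270, which itself pulls the common-set HR below the treated-only value.

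**The case against.** The strongest reply is that the bias needs a step the plan never states. Untreated patients have no LSN-to-tPA time. The median may simply use observed times, and the Cox model may drop patients without one. In either case nothing is distorted. This stands: what is shown is an arm-specific population with a missing rule, not an analysis that must be biased. But the parenthesis about SM weeks has no function if untreated SM patients are excluded, and a model run like survival would naturally keep them as censored.

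Second, untreated eligible patients are probably rarer on the MSU. The causes named in Protocol 5.C.4 for SM arise from delay, while Protocol 5.C.3 names access or technical failure. Appendix 5 adds an intraosseous route after failed IV access. Protocol 5.C.3 speaks only of tPA given on board, so a patient treated later in the ED may still count as treated. This also stands, and it is why the low-share figures come first. The share is still not zero by design, because a blinded adjudicator may find eligible a patient whom the on-scene neurologist chose not to treat.

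Third, the sentence on the second analysis names no arm, so the row above 270 minutes may have been meant for both. That is fair, and the problem with that row exists only if the arm-specific note governs it.

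A reader might also infer that the primary cohort is tilted, because SM eligibility is settled after ED assessment. The documents do not support that reading. Protocol 5.C.4 keeps SM patients who resolve or run late, and ED assessment is where SM labs and CT take place. Only the mention of clinical re-evaluation in the synopsis, Protocol 5.A and SAP 2.1 sits awkwardly with this, and that is a separate wording matter.

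**Conclusion.** The point holds as a specification fault in one secondary outcome and should be fixed. The population differs by arm in all three places where it is defined, and no rule says what happens to untreated patients. If untreated SM patients are kept and untreated MSU patients are not, the result leans toward MSU; none of the handlings tried leaned toward SM.

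At the low MSU untreated shares the documents suggest (0 to 1%), the HR is inflated by a factor of 1.00 to 1.05 with censoring at 270 minutes, or 1.00 to 1.01 with ED-time censoring. The figures of about 1.23 and 1.42 (or 1.05 and 1.11) are upper illustrations that assume 5% and 10% untreated in both arms, and should not be read as the expected bias. All sizes rest on assumed shares, time distributions and censoring rules.

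It would be wrong to infer that the trial's evidence on speed is unreliable as a whole. The primary outcome, percent treated and the time-to-decision outcomes each use one population rule in both arms, and a true 25-minute gain keeps its direction.

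**What to change.** In the Protocol synopsis, Protocol 6.A.4 and SAP 2.2.2:

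- Use all adjudicated tPA-eligible patients in both arms for the Cox and categorical analyses.
- State one censoring rule for untreated patients in Protocol 7.C and SAP 5.1.4, and apply it in both arms.
- Fill the row above 270 minutes from both arms, only with patients untreated because it was too late, and add a row for other reasons.
- Report the median, and a sensitivity analysis, on treated patients in both arms.

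The cost is wording, with no extra patients. LSN and bolus times are already on the list of collected data. A field for the reason tPA was not given may be needed, since Protocol 5.D says a miss is noted but not that its reason is recorded.

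The price is a smaller estimated time gain: slightly smaller at low untreated shares, but substantially smaller if many are untreated and all are censored at 270 minutes. That is why the treated-only result should be shown beside it, with the caution that it conditions on something that happens after allocation.

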2.2.3. Safety Outcomes

- The incidence of symptomatic intracranial hemorrhage (sICH) in enrolled tPA treated patients on MSU weeks compared to SM weeks (Symptomatic intracranial hemorrhage defined as any intracranial blood accumulation associated with a clinical deterioration of ≥ 4 points of the NIHSS for which the hemorrhage has been identified as the dominating cause of the neurologic deterioration) N.B. Patients will include all patients treated with tPA, whether or not they meet all inclusion and exclusion criteria.
- Mortality. N.B. All enrolled patients signing informed consent will be included in this endpoint and followed until 1 year.
- The incidence of stroke mimics and transient ischemic attacks (TIAs) in tPA-treated patients, and also in tPA-eligible patients, on MSU weeks compared to SM weeks. N.B. SM patients deemed eligible for tPA on their pre-hospital assessment who then completely recover by the time of arrival in the ED will equal the excess incidence of TIAs treated on the MSU pathway.

